## **8 HUMAN SUBJECTS PROTECTIONS**

### **8.1 RATIONALE FOR SUBJECT SELECTION**

Participants will be invited to enroll onto this trial if they are an adult and meet the eligibility criteria outlined in section [2.1](#). No gender, racial or ethnic groups will be excluded from participation in this trial. Adults who are cognitively impaired prior to study entry will not be eligible for study entry because they cannot give informed consent.

### **8.2 PARTICIPATION OF CHILDREN**

Children are not eligible for this protocol therapy due to the very different biology and clinical behavior of childhood malignancies. Normal tissue response and toxicity is significantly different as well given that many normal tissues are still growing and developing. In addition, the oncologic practice in childhood malignancies is to avoid high-dose brachytherapy procedures.

### **8.3 EVALUATION OF BENEFITS AND RISKS/DISCOMFORTS**

All procedures/tests in this protocol are used routinely in standard care settings with minimal associated risks and/or discomforts. Participants on this study will be receiving treatment for their malignancy per standard of care. There are no direct medical benefits expected from taking part in this study. We hope the information learned from this study will benefit participants in the future.

The risks and benefits of each procedure/test, as well as the implications of the procedure/test results will be discussed thoroughly with the participant prior to the intervention. Specific risks and potential complications of each procedure will be outlined in a consent form. When the procedure/test poses any risk to the participant, an additional consent will be obtained.

#### **8.3.1 Radiation risk**

Likely medical risks include fatigue, low blood counts and skin reactions at the radiation site. Rare medical risks associated with brachytherapy include infection, bleeding, and perforation of the treated organ or surrounding organs and development of new cancer.

Participants' tumors may be exposed to up to 15 Gy of radiation from High Dose Rate Brachytherapy. Participants will also receive a much smaller amount of radiation from scans used to plan treatment and measure progress. The total scans include up to 4 CT scans.

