#### 2.1.1.6.4 Prostate Cancer

- Participants with localized prostate cancer (T1b-T3b) in whom brachytherapy will be integrated as a boost to external beam radiation or used as monotherapy for definitive management.

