#### 3.2.2.2 Applicator/ Catheter Placement Procedure

- If the participant is to receive sedation, instruction will be given per the anesthesia department.
- The participant will arrive in the ROB clinic the morning of the procedure and be prepared for the HDR procedure by the ROB staff.
- In diseases where catheters have been previously placed at the time of surgery (i.e., breast cancer), the participant will arrive with catheters in place. Otherwise, the participant will be positioned, the area cleansed with an antimicrobial solution and draped according to standard sterile technique. Brachytherapy applicators or catheters are inserted in anatomical sites defined by the physician and secured by sutures or packing as needed.
- If the site can be imaged, ultrasound or CT images will again be obtained.
- The placement of the applicators may be adjusted as needed based on the images until the radiation oncologists are satisfied with applicator placements.

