### **2. Implant Dosimetry And Treatment Planning And Dosage Recommendations**

A minimum of 7mm between the skin and balloon should be maintained. During the planning process, normal tissue doses will be respected and a three-dimensional calculation with DVH-based analysis should be created. Breast dose parameters should include V100, V150, and V200. Skin dose parameters should include Dmax. (6)

- Target coverage:  $\geq 90\%$  of the dose delivered to  $\geq 90\%$  of the target volume
- V150: balloon catheter  $< 50 \text{ cm}^3$
- V200: balloon catheter  $< 10 \text{ cm}^3$
- DHI  $\geq 0.75$  where DHI =  $(1 - V150/V100)$
- Maximum skin isodose: balloon catheter  $< 145\%$
- Primary treatment 34 Gy in 10 fractions over 5 treatment days

If treatment is being delivered as the primary treatment then it should be given as 34 Gy in 10 fractions over 5 days. Treatment should be administered either before or after chemotherapy (if persistent cavity or surgical clips placed). If chemotherapy will be administered, then the recommendation is to wait  $>2$  weeks after completion of APBI before initiating (6)

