## **E. Prostate**

### **1. Technique and dosage recommendations**

Definitive boost therapy: For definitive boost therapy, a single HDR brachytherapy implant (1500 cGy/implant) will be delivered within 21 days of a course of external beam radiotherapy (4600 cGy, 2Gy/day or 4500 cGy, 1.8 Gy/day). Alternative fractionation schedules include 9.5 Gy- 11.5 Gy x 2 fractions, 5.5-7.5 Gy x 3, and 4.0-6.0 Gy x 4 fractions. These regimens are those described in the ABS and NCCN guidelines.

Definitive monotherapy: The regimen chosen will be based on participant and tumor factors. For definitive monotherapy, doses of 12-13.5 Gy x 2 fractions, 9.5 Gy x 4, 10.5 Gy x 3 are described by the NCCN and ABS as appropriate monotherapy doses and will be options for treatment on this protocol.

Salvage: For salvage, participants will receive 8 Gy x 4 fractions without external beam irradiation.

Simulation: Participants will undergo CT simulation for the external beam portion of treatment as per routine in the supine position. For EBRT the planning target volume (PTV) will be defined as the clinical target volume (CTV) plus a margin defined by the treating physician. The external beam component will be delivered in one phase. Treatment planning goals are to try to achieve an isodose distribution where the PTV is covered by at least the 90% isodose line, and the 100% isodose line encompasses the CTV. Doses will be prescribed to the 100% isodose line.

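### Section 8.3.1 gives 15 Gy as the HDR maximum for every participant, but Appendix A lists course doses up to 25 to 48 Gy by site; the limit of four CT scans may also be too low

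*Combined protocol and SAP*

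**What the plan says.** Section 8.3.1 (Radiation risk) addresses all participants, whatever the tumor site. It says their "tumors may be exposed to up to 15 Gy of radiation from High Dose Rate Brachytherapy". After mentioning the smaller exposure from scans used for planning and for measuring progress, it adds "The total scans include up to 4 CT scans". Neither sentence is limited to a site, a fraction or an implant.

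Appendix A sets out the HDR schedules, almost all of them multi-fraction:

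- **Prostate.** One boost option is "a single HDR brachytherapy implant (1500 cGy/implant) will be delivered", which is 15 Gy. Monotherapy options are "doses of 12-13.5 Gy x 2 fractions, 9.5 Gy x 4, 10.5 Gy x 3". A salvage schedule is also listed: "For salvage, participants will receive 8 Gy x 4 fractions without external beam irradiation".
- **Breast.** The only schedule listed is "Primary treatment 34 Gy in 10 fractions over 5 treatment days".
- **Cervix, endometrium and lung.** Tables or lists give between two and eight fractions.

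On imaging, section 3.2.2.3 uses CT for final planning where the target can be imaged, with ultrasound for prostate. Section 3.4.2 sets follow-up at 1, 3, 6, 9 and 12 months, lists imaging among the evaluations, and prefers CT when the lesion is visible on it.

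**The concern.** A reader of 8.3.1 would take 15 Gy as the most HDR radiation any participant can receive on the study. The wording invites this, because the next figure in the same paragraph is a total count of scans. Appendix A allows more than that in every stratum, and for breast the only listed schedule is more than double it.

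What is at stake is the accuracy of the risk statement. Section 10.3 gives no toxicity information of its own and refers back to 8.3, and section 8.3 says risks will be set out in a consent form. The consent form is not among the documents available here, so whether it repeats 15 Gy or four CT scans cannot be checked.

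**Working it through.** **Dose.** Inputs are the fractions and dose per fraction in Appendix A, parts A to E, counting HDR only and excluding external beam. Course total = number of fractions × dose per fraction. Both ends of each prostate dose range are counted as entries.

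| Site | Course totals (Gy) | Above 15 Gy | Maximum | Maximum ÷ 15 |
|---|---|---|---|---|
| Cervix | 45, 45.5, 48, 30, 31.8; 32.5, 34.8, 28, 30, 31.8 | 10 of 10 | 8 × 6.0 = 48 | 3.2 |
| Endometrium | 21, 22, 23.5, 32.4, 31.5, 35.2, 37.5; 11, 12, 16, 18; 34, 36.5, 38.4, 39.9; 17, 18.9, 20.8; 21, 24, 30, 28 | 20 of 22 | 7 × 5.7 = 39.9 | 2.66 |
| Lung | 22.5, 20, 24; 15, 15; 25, 22.5 | 5 of 7 | 5 × 5 = 25 | 1.67 |
| Breast | 34 | 1 of 1 | 34 | 2.27 |
| Prostate | 15; 19, 23, 16.5, 22.5, 16, 24; 24, 27, 38, 31.5; 32 | 11 of 12 | 4 × 9.5 = 38 | 2.53 |

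In total 10 + 20 + 5 + 1 + 11 = 47 of 52 entries exceed 15 Gy. The five that do not are two endometrial boosts (11 and 12), two lung boosts (15 and 15) and the single-implant prostate boost (15). The stated figure is therefore reproduced as a course total only by that prostate boost and the two lung boosts.

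Other ways of counting:

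| Count | Above 15 Gy |
|---|---|
| Each prostate range counted once | 43 of 48 |
| Duplicate schedules within a site removed | 43 of 48 |
| Cervix held to six fractions, as the text above its tables says (drops 7 × 6.5 and 8 × 6.0; maximum becomes 6 × 7.5 = 45 Gy, 3.0 times) | 45 of 50 |
| Prostate salvage dropped | 46 of 51 |
| Both of the last two | 44 of 49 |
| Postoperative rows dropped (11 adjuvant endometrial, 9 of them above 15 Gy, and 1 breast): 47 − 10 of 52 − 12 | 37 of 40 |

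Dropping salvage is worth trying because the prostate inclusion criterion covers only participants "in whom brachytherapy will be integrated as a boost to external beam radiation or used as monotherapy for definitive management".

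**Alternative units.**

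- *Per fraction.* 51 of 52 entries are at or below 15 Gy. The exception is the endometrial row of 2 × 16.2 Gy at the vaginal surface. It carries an asterisk whose footnote is not visible.
- *Per implant.* This matches the unit Appendix A attaches to the prostate boost. For breast, section 3.2.2.2 says "the participant will arrive with catheters in place" and Appendix A gives 34 Gy over 5 days, so one implant appears to deliver 34 Gy.

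**CT scans.** For a target both planned and followed by CT:

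- one planning CT + five follow-up visits (months 1, 3, 6, 9, 12; section 3.4.2) = 6
- one planning CT + four 3-monthly assessments (section 3.1) = 5

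Both exceed 4. Baseline CT (which may fall under the separate screening protocol), pre-plan CT and CTs at repeat insertions are not counted and would add to this.

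**The case against.** The strongest reply is that a unit has dropped out and the maximum itself is not false. Appendix A writes the same 15 Gy per implant, and per fraction it fits every entry but one. That one is a postoperative mucosal-surface dose with an unseen footnote, which is arguably not a tumor dose at all. This is plausible, and the 16.2 Gy row should carry little weight. But nothing in section 8 supplies the unit. If it were supplied, a participant facing ten fractions would still not be told the course dose, and the per-implant reading still appears to fail for breast.

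Three further objections stand in part:

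- **The count.** Table rows are not participants, and the totals are summed across different prescription points (surface, 0.5 cm, 1 cm, 2 cm). The ratios are therefore not risk multiples. The conclusion needs only the site maxima, which do not depend on how rows are counted.
- **The ceilings.** Section 3.2.2.4 calls the doses suggested, section 3.3 leaves changes to the radiation oncologist, and the cervix text and table disagree on the number of fractions. The maxima here are the highest listed schedules, not hard limits.
- **The CT figure.** MRI or other imaging may replace CT, pre-planning may use ultrasound, and prostate uses ultrasound planning with PSA follow-up. The conflict is conditional and leaves those participants largely unaffected.

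It is also true that the ethics board sees Appendix A and that treatment follows it. That protects the delivered dose but does not correct the risk statement.

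**Conclusion.** The concern holds. As written, the HDR figure in 8.3.1 is below the highest listed course dose in every stratum, by a factor of 1.7 (lung) to 3.2 (cervix; 3.0 if held to six fractions). This rests on reading an unqualified maximum as a course total. If 15 Gy was meant per fraction or per implant, the fault becomes a missing unit and an unstated cumulative dose, and the sentence still needs correcting. The CT limit is too low by one or two scans for participants planned and followed by CT, assuming imaging at each scheduled assessment. Nothing in the endpoints, sample size or error rates changes.

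**What to change.** In 8.3.1, replace 15 Gy with the highest HDR course dose listed in Appendix A for each stratum: gynecologic 48 Gy (45 Gy if cervix is limited to six fractions), lung 25 Gy, breast 34 Gy, prostate 38 Gy. Settle the cervix fraction limit first, since the gynecologic figure depends on it. If 15 Gy is kept as a per-fraction figure, say so, note the 16.2 Gy endometrial row as an exception, and still give the course total.

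Restate the CT maximum for CT-followed participants to match 3.2.2 and 3.4.2, or state at which visits CT is not intended. Check that the consent form agrees on both figures.

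The cost is two sentences in a routine amendment, plus the consent form if it repeats the numbers. The stated exposure becomes less favourable. Data collection and analysis do not change.

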#### **8.3.2 Imaging risk**

Participants may feel discomfort from lying still during imaging. Some participants may also experience claustrophobia.

#### **8.3.3 Contrast risk**

Participants may experience an allergic reaction to contrast used during imaging. For participants that undergo an MRI with gadolinium, there is a risk for nephrogenic systemic

fibrosis for participants with kidney disease. Some participants may also have gadolinium retention. Participants with abnormal kidney function will not have an MRI with gadolinium.

#### 8.3.4 Blood draw risk

Blood draws may cause pain, redness, bruising or infection at the site of the needle stick. Rarely some participants faint.

#### 8.3.5 Anesthesia risk

8.3.6 The risks associated with anesthesia are nausea, vomiting, headache and back pain. Other less likely but serious risks include blood pressure problems, arrhythmias, respiration changes, allergic reactions, paralysis, heart attack, stroke, or death. High dose rate brachytherapy implants

Risks associated with implants are pain and discomfort.

### **8.4 INFORMED CONSENT PROCESS AND DOCUMENTATION**

The informed consent document will be provided to the participant for review prior to consenting. A designated study investigator will carefully explain the procedures and tests involved in this study, and the associated risks, discomforts and benefits. In order to minimize potential coercion, as much time as is needed to review the document will be given, including an opportunity to discuss it with friends, family members and/or other advisors, and to ask questions of any designated study investigator. A signed informed consent document will be obtained prior to entry onto the study.

The initial consent process as well as re-consent, when required, may take place in person or remotely (e.g., via telephone or other NIH approved remote platforms) per discretion of the designated study investigator and with the agreement of the participant. Whether in person or remote, the privacy of the subject will be maintained. Consenting investigators will be located in a private area (e.g., clinic consult room). When consent is conducted remotely, the participant will be informed of the private nature of the discussion and will be encouraged to relocate to a more private setting if needed.

### **8.5 PARTICIPANT ADVOCATE**

The participant's rights representative is available to participants on this protocol at [contact] in [name], NIH. Participants may ask any questions about the study and may withdraw their consent at any time without compromising their medical care.

## **9 REGULATORY AND OPERATIONAL CONSIDERATIONS**

### **9.1 STUDY DISCONTINUATION AND CLOSURE**

This study may be temporarily suspended or prematurely terminated if there is sufficient reasonable cause. Written notification, documenting the reason for study suspension or termination, will be provided by the suspending or terminating party to study participants, investigator, and regulatory authorities. If the study is prematurely terminated or suspended, the Principal Investigator (PI) will promptly inform study participants, the Institutional Review Board (IRB), and will provide the reason(s) for the termination or suspension. Study participants will be contacted, as applicable, and be informed of changes to study visit schedule.

Circumstances that may warrant termination or suspension include, but are not limited to:

- Determination of unexpected, significant, or unacceptable risk to participants
- Insufficient compliance to protocol requirements
- Data that are not sufficiently complete and/or evaluable
- Determination that the primary endpoint has been met

Study may resume once concerns about safety, protocol compliance, and data quality are addressed, and satisfy the IRB.

## **9.2 QUALITY ASSURANCE AND QUALITY CONTROL**

Each clinical site will perform internal quality management of study conduct, data and biological specimen collection, documentation and completion. An individualized quality management plan will be developed to describe a site's quality management.

Quality control (QC) procedures will be implemented beginning with the data entry system and data QC checks that will be run on the database will be generated. Any missing data or data anomalies will be communicated to the site(s) for clarification/resolution.

Following written Standard Operating Procedures (SOPs), the monitors will verify that the clinical trial is conducted and data are generated and biological specimens are collected, documented (recorded), and reported in compliance with the protocol, International Conference on Harmonisation Good Clinical Practice (ICH GCP), and applicable regulatory requirements (e.g., Good Laboratory Practices (GLP), Good Manufacturing Practices (GMP)).

The investigational site will provide direct access to all trial related sites, source data/documents, and reports for the purpose of monitoring and auditing by the sponsor, and inspection by local and regulatory authorities.

## **9.3 CONFLICT OF INTEREST POLICY**

The independence of this study from any actual or perceived influence, such as by the pharmaceutical industry, is critical. Therefore, any actual conflict of interest of persons who have a role in the design, conduct, analysis, publication, or any aspect of this trial will be disclosed and managed. Furthermore, persons who have a perceived conflict of interest will be required to have such conflicts managed in a way that is appropriate to their participation in the design and conduct of this trial. The study leadership in conjunction with the National Cancer Institute has established policies and procedures for all study group members to disclose all conflicts of interest and will establish a mechanism for the management of all reported dualities of interest.

## **9.4 CONFIDENTIALITY AND PRIVACY**

Participant confidentiality and privacy is strictly held in trust by the participating investigators and their staff. This confidentiality is extended to cover testing of biological samples and genetic tests in addition to the clinical information relating to participants. Therefore, the study protocol, documentation, data, and all other information generated will be held in strict confidence.

All research activities will be conducted in as private a setting as possible.

The study monitor, representatives of the Institutional Review Board (IRB), and/or regulatory agencies may inspect all documents and records required to be maintained by the investigator,

including but not limited to, medical records (office, clinic, or hospital) and pharmacy records for the participants in this study. The clinical study site will permit access to such records.

The study participant's contact information will be securely stored at the/each clinical site for internal use during the study. At the end of the study, all records will continue to be kept in a secure location for as long a period as dictated by the reviewing IRB and Institutional policies.

Study participant research data, which is for purposes of statistical analysis and scientific reporting, will be stored at the NCI CCR. This will not include the participant's contact or identifying information. Rather, individual participants and their research data will be identified by a unique study identification number. The study data entry and study management systems used by the clinical site(s) and by NCI CCR research staff will be secured and password protected. At the end of the study, all study databases will be archived at the NIH.

To further protect the privacy of study participants, a Certificate of Confidentiality has been issued by the National Institutes of Health (NIH). This certificate protects identifiable research information from forced disclosure. It allows the investigator and others who have access to research records to refuse to disclose identifying information on research participation in any civil, criminal, administrative, legislative, or other proceeding, whether at the federal, state, or local level. By protecting researchers and institutions from being compelled to disclose information that would identify research participants, Certificates of Confidentiality help achieve the research objectives and promote participation in studies by helping assure confidentiality and privacy to participants.

## **10 COMMERCIAL DEVICE INFORMATION**

### **10.1 RADIATION**

There will be no IDE obtained for the use of any of the commercial agents used in this study.

This study meets the criteria under category #1 for exemption for an IDE as this investigation involves the use of an already cleared medical device in which the device is used or investigated in accordance with the indications in the cleared labeling.

### **10.2 SOURCE**

The radiation device is a commercial device that will be located in the NIH Clinical Center.

### **10.3 TOXICITY**

Refer to section [8.3](#).

### **10.4 ADMINISTRATION PROCEDURES**

Refer to section [3.2](#).

## 12 APPENDICES

### 12.1 APPENDIX A: SUGGESTED DOSES FOR BRACHYTHERAPY ADMINISTRATION PER ABS GUIDELINES

#### A. Cervical Cancer

##### 1. Technique

Three to six HDR treatments will be delivered, based on host factors (inability to tolerate treatment, changes in physical findings, poor anatomy for implant) as well as the discretion of the treating radiation oncologists. Packing, followed by brachytherapy applicators, will then be removed, and the participants recovered in the PACU, where supportive care may include analgesia, antibiotics, and douches with hydrogen peroxide and water etc., may be delivered. HDR brachytherapy is an outpatient procedure, though very rarely, participants may be admitted overnight for observation.

Implants may be delivered either during or following the EBRT, with the goal of keeping the total duration of treatment to fewer than 8 weeks when possible because of the effect of prolonged treatment duration and decreased survival (4)

Per ABS guidelines, for early cervical cancer, the following guidelines will be adhered to:

EBRT (Gy) @ 1.8 Gy/fraction	No. of HDR fractions	HDR dose/fraction
20	6	7.5
20	7	6.5
20	8	6.0
45	5	6.0
45	6	5.3

Per ABS guidelines, for advanced cervical cancer, the following guidelines will be adhered to:

EBRT (Gy) @ 1.8 Gy/fraction	No. of HDR fractions	HDR dose/fraction
45	5	6.5
45	6	5.8
50.4	4	7.0
50.4	5	6.0
50.4	6	5.3

(5)

